1.2 Recruitment extension

Given the massive challenges to identify the trial population, the recruitment period is extended with 8 weeks (i.e. in total 24 weeks) in order to allow sufficient time for recruitment.

In this protocol amendment:

- Any new text is written *in italics*.
- Any text deleted from the protocol is written using ~~strike through~~.

2 Changes

1 Summary

1.4 Key inclusion criteria

- Male or female Japanese subjects, age ≥ 20 years at the time of signing informed consent T2DM subjects (diagnosed clinically) ≥ 6 months prior to screening
- HbA1c 7.5-11.0% [58 mmol/mol-97 mmol/mol] (both inclusive) by central laboratory analysis
- Subjects on stable daily insulin doses for at least ~~60~~ 90 days prior to screening administered once or twice daily, either as basal insulin (e.g. IDeg, insulin glargine, insulin detemir, NPH insulin) or pre-mix/combination insulin (e.g. biphasic insulin aspart, insulin degludec/insulin aspart). Total daily insulin dose in the previous ~~60~~ 90 days should be within 20-50 units, both inclusive, and on the day of screening, but fluctuations of ± 20 ~~10~~% within the ~~60~~ 90 days prior to screening are acceptable. The specified insulin treatment should be administered in combination
 - with a stable daily dose of metformin within current approved Japanese label for at least ~~60~~ 90 days prior to screening,

- additionally, the anti-diabetic treatment can be with or without a stable daily dose of one of the following other OADs: SU, glinides, α -GI, SGLT2i or TZD within current approved Japanese label for at least ~~60~~ 90 days prior to screening
- Body Mass Index (BMI) ≥ 23 kg/m²

1.5 Key exclusion criteria

- Receipt of any investigational medicinal product (IMP) within 30 days before screening
- Use of any anti-diabetic drug in a period of ~~60~~ 90 days before screening (except pre-mix/combination or basal insulin, metformin, SU, glinides, α -GI, SGLT2i, or TZD) or anticipated change in concomitant medication, which in the investigators opinion could interfere with glucose metabolism (e.g. systemic corticosteroids or bolus insulin)
- *Treatment with glucagon-like peptide-1 (GLP-1) receptor agonist during the last 60 days prior to screening and furthermore, the discontinuation of GLP-1 receptor agonist at any point in time must not have been due to safety concerns, tolerability issues or lack of efficacy, as judged by the investigator* ~~Previous treatment with glucagon-like peptide-1 (GLP-1) receptor agonists~~
- Treatment with dipetidyl peptidase-4 (DPP-4) inhibitors during the last ~~60~~ 90 days prior to screening
- Impaired liver function, defined as alanine aminotransferase (ALT) or aspartate aminotransferase (AST) ≥ 2.5 times upper limit of normal
- Renal impairment estimated Glomerular Filtration Rate (eGFR) < 60 mL/min/1.73m² as per Chronic Kidney Disease Epidemiology Collaboration (CKD-EPI)
- Screening calcitonin ≥ 50 ng/L
- History of pancreatitis (acute or chronic)
- Personal or family history of medullary thyroid carcinoma (MTC) or multiple endocrine neoplasia type 2 (MEN 2)
- Subjects presently classified as being in New York Heart Association (NYHA) Class IV

5 Trial design

5.5 Rationale for treatment

Pre-trial insulin and OAD treatment should be in accordance with current Japanese approved labelling. Subjects should be on at least ~~60~~ 90 days of stable treatment (insulin and OADs) defined as unchanged medication and unchanged dose. To reduce the risk of hypoglycaemia all other OADs apart from metformin will be discontinued at randomisation. After randomisation metformin treatment should remain unchanged during the trial, however in case of safety concerns the dose may be reduced at the discretion of the investigator. To avoid impact on trial objectives, no other

treatments affecting weight, glucose or lipid should be used, and certain drugs should not be used before the trial (see exclusion criteria no. 5, 6 and 7).

6 Trial population

6.1 Inclusion criteria

For an eligible subject, all inclusion criteria must be answered “yes”.

1. Informed consent obtained before any trial-related activities. Trial-related activities are any procedures that are carried out as part of the trial, including activities to determine suitability for the trial.
2. Male or female Japanese subjects ≥ 20 years of age at the time of signed informed consent.
3. Type 2 diabetes mellitus subjects (diagnosed clinically) ≥ 6 months prior to screening.
4. HbA1c 7.5-11.0% [58 mmol/mol-97 mmol/mol] (both inclusive) by central laboratory analysis.
5. Subjects on stable daily insulin doses for at least ~~60~~ ~~90~~ days prior to screening administered once or twice daily according to current Japanese label, either as basal insulin (e.g. IDeg, insulin glargine, insulin detemir, NPH insulin), or pre-mix/combination insulin (e.g. biphasic insulin aspart, insulin degludec/insulin aspart). Total daily insulin dose in the previous ~~60~~ ~~90~~ days should be within 20-50 units, both inclusive, and on the day of screening, but fluctuations of $\pm 20\%$ within the ~~60~~ ~~90~~ days prior to screening are acceptable. The specified insulin treatment should be administered in combination
 - with a stable daily dose of metformin within current approved Japanese label for at least ~~60~~ ~~90~~ days prior to screening,
 - additionally, the anti-diabetic treatment can be with or without a stable daily dose of one of the following other oral anti-diabetic drugs: sulphonylureas (SU), glinides, α -glucosidase inhibitors (α -GI), sodium-glucose co-transporter-2 inhibitors (SGLT2i) or thiazolidinediones (TZD) within current approved Japanese label for at least ~~60~~ ~~90~~ days prior to screening.
6. Body Mass Index (BMI) ≥ 23 kg/m².

Rational for inclusion criteria:

- Criterion 1 is applied through an ethical consideration, in accordance with the GCP¹
- Criterion 2 is applied to exclude minors through an ethical consideration. Subjects aged 65 year or older are included in accordance with the ICH guideline: Studies in support of special populations: Geriatrics¹²
- Criteria 3 and 4 are chosen according to the objective of the trial. Being diagnosed for 6 months or more is required in order to ensure correct diagnosis and metabolic stabilisation. HbA1c range (7.5-11.0 %) is chosen to include subjects whose glycaemic control is not adequate on pre-trial treatment and intensification is considered possible. The upper limit of HbA1c is

chosen in order to exclude subjects with unacceptable glycaemic control who need a more intensive therapy.

- Criterion 5 is applied to ensure that the subject's glycaemic control is stabilised at randomisation. 60 ~~90~~ days of unchanged pre-trial treatment are required.
- Criterion 6 is chosen in order to ensure a population allowing for exploring the full dose range of IDegLira, and to minimize the individual impact of any weight loss that may be associated with IDegLira treatment.

6.2 Exclusion criteria

For an eligible subject, all exclusion criteria must be answered “no”.

1. Known or suspected hypersensitivity to trial product(s) or related products.
2. Previous participation in this trial. Participation is defined as signed informed consent.
3. Female who is pregnant, breast-feeding or intends to become pregnant or is of child-bearing potential and not using adequate contraceptive methods (e.g., abstinence, diaphragm, condom [by the partner], intrauterine device, sponge, spermicide or oral contraceptives).
4. Receipt of any investigational medicinal product (IMP) within 30 days before screening.
5. Use of any anti-diabetic drug in a period of 60 ~~90~~ days before screening (except pre-mix/combination insulin or basal insulin, metformin, sulphonylureas (SU), glinides, α -glucosidase inhibitors (α -GI), sodium-glucose co-transporter-2 inhibitors (SGLT2i), or thiazolidinediones (TZD) or anticipated change in concomitant medication, which in the investigators opinion could interfere with glucose metabolism (e.g. systemic corticosteroids or bolus insulin).
6. *Treatment with glucagon-like peptide-1 (GLP-1) receptor agonist during the last 60 days prior to screening and furthermore, the discontinuation of GLP-1 receptor agonist at any point in time must not have been due to safety concerns, tolerability issues or lack of efficacy, as judged by the investigator.* ~~Previous treatment with glucagon-like peptide-1 (GLP-1) receptor agonist.~~
7. Treatment with dipetidyl peptidase-4 (DPP-4) inhibitors during the last 60 ~~90~~ days prior to screening.
8. Impaired liver function, defined as alanine aminotransferase (ALT) or aspartate aminotransferase (AST) ≥ 2.5 times upper limit of normal (UNL).
9. Renal impairment estimated glomerular filtration rate (eGFR) $< 60 \text{ ml/min/1.73m}^2$ as per Chronic Kidney Disease Epidemiology Collaboration (CKD-EPI).
10. Screening calcitonin $\geq 50 \text{ ng/L}$.
11. History of pancreatitis (acute or chronic).
12. Personal or family history of medullary thyroid carcinoma (MTC) or multiple endocrine neoplasia syndrome type 2 (MEN 2).
13. Subjects presently classified as being in New York Heart Association (NYHA) Class IV.
14. Within the past 180 days have had any of the following: myocardial infarction (MI), stroke or hospitalisation for unstable angina and/or transient ischemic attack (TIA) prior to screening.

15. Inadequately treated blood pressure as defined as Class 2 hypertension or higher (Systolic \geq 160 mmHg or diastolic \geq 100 mmHg) in accordance with National High Blood Pressure Education Program, 7th Joint National Committee and European Societies of Hypertension/Cardiology 2013 guidelines¹³.
16. Proliferative retinopathy or maculopathy requiring acute treatment as verified by fundoscopy or fundus photography performed within 90 days prior to randomisation.
17. Diagnosis of malignant neoplasms within the last 5 years (except basal and squamous cell skin cancer, polyps and in-situ carcinomas) prior to screening.
18. Any condition that in the opinion of the investigator might jeopardise subject's safety or compliance with the protocol.

7 Milestones

Planned duration of recruitment period (first patient first visit (FPFV) – last patient first visit (LPFV): ~~244~~ weeks.

End of trial is defined as last patient last visit (LPLV).

IDegLira
Trial ID: NN9068-4184
Clinical Trial Report

1.1 Trial information

This phase 3 trial is a 26-week randomised, parallel two-arm, double-blinded, multi-centre, treat-to-target trial in Japanese subjects with T2DM inadequately controlled with basal insulin or pre-mix/combination insulin, combined with metformin with or without one of the following OADs: SU, glinides, α -GI, SGLT2i or TZD, hereafter collectively referred to as other OADs. The trial is comparing efficacy and safety of insulin degludec/liraglutide (IDegLira) versus insulin degludec (IDeg) both in combination with Metformin. For further details please see the protocol.

1.2 Scope of the statistical analysis plan

This Statistical Analysis Plan (SAP) is based on Final Protocol version 4.0 (15-Dec-2016).

The scope of this SAP is to specify the statistical analysis for change from baseline in body weight after 26 weeks of treatment and add sensitivity analysis for change from baseline in HbA_{1c} after 26 weeks of treatment due to protocol amendment 2 during recruitment of subjects. Furthermore, some errors have been corrected. For further details on the changes see [section 3](#).

2 Statistical considerations

Novo Nordisk will analyse and report data from all sites together.

All analyses of efficacy and safety endpoints will be based on the full analysis set (FAS). All efficacy endpoints will be summarised using the FAS and safety endpoints will be summarised using the safety analysis set (SAS).

The impact of protocol deviations and outliers may be investigated further in the sensitivity analyses if deemed relevant.

Unless otherwise specified, all continuous measurements will be summarised descriptively at each visit by treatment using observed data. After 26 weeks of treatment, descriptive statistics will be presented based both on observed and last observation carried forward (LOCF) imputed data. Endpoints that are analysed untransformed and endpoints that are not formally analysed are summarised by the arithmetic mean, standard deviation (SD), median, and minimum and maximum values. Endpoints that are analysed log-transformed are supplemented with the geometric mean and coefficient of variation (CV).

For measurements over time, mean values will be plotted to explore the trajectory over time. LOCF imputed data will be used as the basis for plotting data, if not otherwise specified. For endpoints that are analysed log-transformed, the geometric mean values will be plotted.

A standard analysis of covariance (ANCOVA) model will be applied for the continuous primary and secondary endpoints. The model includes treatment, pre-trial anti-diabetic treatment (metformin + basal insulin, metformin + one other OAD + basal insulin, metformin + pre-mix/combination insulin, metformin + one other OAD + pre-mix/combination insulin) as fixed factors and the corresponding baseline value as covariate. In the following, this model will be referred to as the standard ANCOVA model.

Presentation of results from a statistical analysis will include the estimated mean treatment effects (Least Square Means [LSMeans]) for absolute values and change from baseline. In addition, estimated mean treatment difference (or ratio) will be presented together with the two-sided 95% confidence interval and corresponding two-sided p-value.

Handling of missing data

The expected percentage of missing data is around 15%. In accordance with industry guidance endpoints will be assessed at frequent visits. If an assessment was made both at screening (V1) and randomisation (V2), and if not otherwise specified, the value from the randomisation visit will be used as the baseline value. If the value measured at the randomisation visit is missing and the assessment also has been made at screening, then the screening value was used as the baseline value.

Missing values (including intermittent missing values) will be imputed using the LOCF method. Subjects without data after randomisation will be included by carrying forward their baseline value. LOCF has been a standard approach in diabetes trials for many years, and was used as the primary analysis in both IDegLira and IDeg phase 3 trials. LOCF is considered to be an appropriate method in the context of treat-to-target trials, where subjects after withdrawal typically continue their therapy using commercially available insulin. In previous treat-to-target trials with IDegLira and IDeg, LOCF has generally provided similar results to alternative methods applied to handle missing data, such as repeated measures models and completer analyses. In this trial, similar sensitivity analyses will be made to examine the robustness of the LOCF method

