8.4.4 Blood pressure

Blood pressure (systolic and diastolic) should be measured after the subject has been resting for at least 5 minutes in a sitting position. It is recommended to use the same arm and preferably the same equipment throughout the trial.

At screening (V1) the blood pressure should be measured three times and all three values should be entered into the eCRF. The mean value will be calculated by the eCRF and must be in accordance with the relevant exclusion criteria (see section [6.2](#)). For the subsequent visits, one measurement needs to be performed. If the investigator suspects white coat hypertension, re-assessment of the blood pressure (as described above) is allowed.

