8.5.5 Pulse

Pulse (beats per minute) should be measured after resting at least 5 minutes in a sitting position and recorded in the eCRF.

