Responder for HbA_{1c} without hypoglycaemic episodes and weight gain after 26 weeks of treatment will be defined as HbA_{1c} < 7.0% or ≤ 6.5% at ET, without treatment emergent severe or BG confirmed symptomatic hypoglycaemic episodes during the last 12 weeks of treatment, and change from baseline in body weight below or equal to zero. Analysis of each of the two responder endpoints will be based on a logistic regression model with treatment and pre-trial anti-diabetic treatment as fixed factors and baseline HbA_{1c} and body weight values as covariates.

Fasting plasma glucose (FPG)

Change from baseline in FPG after 26 weeks of treatment will be analysed using the standard ANCOVA model.

Waist circumference

Change from baseline in waist circumference after 26 weeks of treatment will be analysed using the standard ANCOVA model.

Blood pressure (systolic and diastolic)

Change from baseline in blood pressure after 26 weeks of treatment will be analysed using the standard ANCOVA model.

Self-measured blood glucose (SMBG) 9-point profile

The following six endpoints from the 9-point profile will be defined:

- 9-point profile (individual SMBG values) [One endpoint]
- Mean of the 9-point profile, defined as the area under the profile (calculated using the trapezoidal method) divided by the measurement time [One endpoint]
- Prandial plasma glucose increments (from before meal to 90 min after for breakfast, lunch and dinner). The mean increment over all meals will be derived as the mean of all available meal increments [Four endpoints]

A linear mixed effect model will be fitted to the 9-point SMBG profile data. The model will include treatment, pre-trial anti-diabetic treatment, time, the interaction between treatment and time and the interaction between pre-trial anti-diabetic treatment and time as fixed factors and subject as random effect. From the model mean profile by treatment and relevant treatment differences will be estimated and explored.

Change from baseline after 26 weeks of treatment in mean of the 9-point profile and post-prandial increment endpoints will be analysed separately using the standard ANCOVA model.

Lipids

Total cholesterol, low density lipoprotein cholesterol (LDL cholesterol), high density lipoprotein cholesterol (HDL cholesterol), very low density lipoprotein cholesterol (VLDL cholesterol),

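### The blood pressure and pulse models adjust for the randomisation-visit value alone; adding the screening value as a second covariate would recover a little precision at almost no cost

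*SAP*

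**What the plan says.** SAP section 2 (Handling of missing data) sets one general baseline rule, which protocol section 17 also contains. When a variable is assessed at both V1 and V2, "the value from the randomisation visit will be used as the baseline value". If the V2 value is missing, "then the screening value was used as the baseline value". The rule leaves room for endpoint-specific exceptions, but none is made for blood pressure or pulse.

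The standard ANCOVA in SAP section 2 has treatment and pre-trial anti-diabetic treatment as factors and "the corresponding baseline value as covariate". SAP 2.4.1.1 applies it without change: "Change from baseline in blood pressure after 26 weeks of treatment will be analysed using the standard ANCOVA model". SAP 2.4.1.2 does the same for pulse.

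On measurement, protocol 8.4.4 says: "At screening (V1) the blood pressure should be measured three times and all three values should be entered into the eCRF". The eCRF computes their mean for the eligibility check. After that, "For the subsequent visits, one measurement needs to be performed", with one exception: "If the investigator suspects white coat hypertension, re-assessment of the blood pressure (as described above) is allowed". For pulse, protocol 8.5.5 says "Pulse (beats per minute) should be measured after resting at least 5 minutes in a sitting position" and describes no replicates; the flow chart marks pulse in its first two columns. The blood pressure row of the flow chart is not readable in the available text, so a V2 measurement is inferred from 8.4.4 and from the change-from-baseline endpoint.

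**The concern.** Blood pressure and pulse vary from occasion to occasion, so a single reading is an imperfect measure of a subject's usual level. A second pre-treatment value, taken at most 14 days earlier (protocol 8.1.5), would help the model explain more of the week-26 variation. It is a legitimate covariate: trial product starts only at or after V2, and pre-trial insulin and other oral drugs stop only at randomisation, so V1 cannot be affected by treatment. It is also already in the database.

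Under the plan, V1 has no role in these models for any subject with a V2 value. For blood pressure, a mean of three readings is left out in favour of what is normally one. What is at stake is the width of the confidence intervals for three supportive comparisons (systolic pressure, diastolic pressure, pulse). The validity of those comparisons is not in question.

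**Working it through.** **The plan's own figures.** The documents give no standard deviation, correlation, interval width or power for blood pressure or pulse. The one precision figure is the HbA1c power. The adjusted difference is 0.85 × 0.45 + 0.15 × 0.20 = 0.4125; with SD 1.0, 105 per arm and a two-sided 5% t-test this gives 84.5%, as in protocol Table 17-1. This point does not touch it.

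**Inputs.** From the documents: three V1 blood pressure readings and normally one at later visits; pulse at V1 and V2; V1 to V2 at most 14 days; 105 subjects per arm. Assumed: V1–V2 correlation ρ = 0.5–0.7, and correlation r of each baseline with week 26 = 0.4–0.6, with r ≤ ρ. The last condition is imposed because two untreated readings within 14 days should agree at least as well as readings before and after 26 weeks of titrated treatment.

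**Step 1: exchangeable visits.** The standard error of the treatment difference is proportional to √(1 − R²). With V2 only, R² = r². With V1 and V2 both as covariates, R² = 2r²/(1 + ρ).

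| r | ρ | R², V2 only | R², both | SE ratio | SE reduction |
|---|---|---|---|---|---|
| 0.4 | 0.7 | 0.160 | 0.32/1.7 = 0.188 | √(0.812/0.840) = 0.983 | 1.7% |
| 0.5 | 0.6 | 0.250 | 0.50/1.6 = 0.3125 | √(0.6875/0.750) = 0.957 | 4.3% |
| 0.6 | 0.6 | 0.360 | 0.72/1.6 = 0.450 | √(0.550/0.640) = 0.927 | 7.3% |

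The first and last rows are the extremes under r ≤ ρ. In the middle row the variance ratio is 0.917, equivalent to 1/0.917 = 1.09, or about 9% more subjects.

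**Step 2: V1 predicts week 26 less well than V2.** With r₁ for V1 and r₂ for V2, R² = (r₁² + r₂² − 2r₁r₂ρ)/(1 − ρ²).

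| r₁ | r₂ | ρ | R², both | SE reduction |
|---|---|---|---|---|
| 0.5 | 0.6 | 0.7 | 0.19/0.51 = 0.373 | 1.0% |
| 0.4 | 0.5 | 0.6 | 0.17/0.64 = 0.266 | 1.0% |
| 0.4 | 0.5 | 0.7 | 0.13/0.51 = 0.255 | 0.3% |

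These are examples, not bounds. With r₂ = 0.6 and ρ = 0.7, r₁ = 0.55 gives R² = 0.2005/0.51 = 0.393 and a 2.6% reduction; r₁ = 0.45 gives 0.1845/0.51 = 0.362 and 0.1%.

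**Step 3: mean of three V1 readings (blood pressure).** Split the variance of one reading into persistent, visit and reading parts; averaging three readings divides the reading part by 3. With assumed shares 0.5/0.25/0.25, residual variance falls from 0.750 to 0.643, so the SE falls by 1 − √(0.643/0.750) = 7.4%, against 5.7% in Step 1 at r = ρ = 0.5. With 0.6/0.2/0.2 it falls from 0.640 to 0.526, a 9.3% reduction, against 7.3% at r = ρ = 0.6. This model assumes V1 is no further from week 26 than V2 in predictive terms, so it is a favourable case.

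**Step 4: bias and eligibility truncation.** A simulation of 2,000 trials used assumed systolic mean 130 and SD 15 mmHg, shares 0.55/0.25/0.20, and the V1 mean required to be below 160 mmHg. The average 95% half-width was 3.39 mmHg with V2 only and 3.14 with both. The average estimated difference was within 0.02 mmHg of the true value of zero under either model.

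**Step 5: price of the extra term.** With 210 subjects, the planned model spends 6 parameters (intercept, treatment, three for pre-trial treatment, baseline), leaving 204 residual degrees of freedom. One more leaves 203. If V1 carried no information, the SE would rise by about √(204/203) − 1 = 0.25%.

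**The case against.** The strongest reply is that nothing here is an error. The last pre-treatment value is a conventional baseline and sole covariate, the ANCOVA is valid under randomisation, and the documents do not contradict each other. Blood pressure and pulse are supportive, are not among the endpoints marked as key, and play no part in the sample size or the superiority conclusion. One uniform model for all continuous endpoints also has some value. All of this stands; it limits the point to an optional gain in precision.

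Several stronger readings are tempting, and the documents do not support them:

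- **That the screening readings are thrown away.** The V1 blood pressure mean decides eligibility, V1 replaces a missing V2, and continuous measurements are summarised at each visit. V1 is missing only as a covariate alongside V2.
- **That the noisiest available reading was chosen.** This is arguable for blood pressure, though white-coat re-assessment can add readings at later visits. It does not hold for pulse, where V1 and V2 are of similar noise.
- **That the gain could approach 10%.** Step 1 with r = 0.6 and ρ = 0.5 gives R² = 0.72/1.5 = 0.48 and a reduction of 1 − √(0.52/0.64) = 9.9%. That requires readings 26 weeks apart, across treatment, to agree better than two untreated readings within 14 days.
- **That HbA1c can be judged in the same way.** The documents give no correlations for it either, and no claim is made.

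The uncertainty over size also stands. If V1 is clearly the weaker predictor, the smallest gains in Step 2 are about the size of the 0.25% price in Step 5.

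**Conclusion.** The point holds as a minor improvement. For subjects with a V2 value, the blood pressure and pulse models leave out a pre-treatment measurement that the trial already collects. The consequence is some lost precision without bias.

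The standard error would fall by about 1.7–7.3% if the visits are exchangeable, ρ is 0.5–0.7 and r is 0.4–0.6 with r ≤ ρ. It would fall by about 0.3–1% in the examples where V1's correlation with week 26 is 0.1 below that of V2. The three-reading mean could push the blood pressure gain above the Step 1 figures. All these correlations are assumptions, and that blood pressure is taken at V2 is itself inferred. The primary analysis and its 84.5% power are unchanged.

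**What to change.** In SAP 2.4.1.1 (systolic and diastolic blood pressure) and 2.4.1.2 (pulse), keep the V2 value as the reference for change from baseline and as a covariate, and add the V1 value as a second covariate. For blood pressure, use the mean of the three V1 readings, which the eCRF already computes. If either V1 or V2 is missing, use the available value for both terms. Record the change in SAP section 3 and fix it before unblinding.

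A second covariate is safer than averaging the two visits, because the model weights V1 by what it contributes. With r₁ = 0.5, r₂ = 0.6 and ρ = 0.7, the simple average made the interval 0.3% wider than V2 alone, while two covariates still narrowed it by 1.0%. The definition of change and the treatment difference being estimated stay the same.

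The cost is one extra term in three supportive models, one degree of freedom of about 200 in each, no new data, and a small departure from the common ANCOVA.
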